6.11. Supportive therapy

- During hospitalization, patients will be cared for in an isolation unit.
- Beginning before conditioning until recovery from severe neutropenia (ANC<500/ μ l) or discharge: oral decontamination and mouth care according to local standards.
- Pentamidine (nebulized) as first line *Pneumocystis jirovecii* prophylaxis from day -30 until complete immunological reconstitution.
- Antibacterial and antifungal prophylaxis according to local standards.

- Acyclovir as Herpes Simplex-prophylaxis until complete immunological reconstitution.
- Intravenous substitution to maintain immunoglobulin IgG >5g/l.
- Hydration of 3L/m² will be given during the conditioning phase (from day -4 to 24 hours after Busulfan).
- CMV (PCR), EBV (PCR) and adenovirus (PCR) viral load will be determined weekly till day +90. If repeatedly negative, after day +90, the interval of testing could be prolonged. Pre-emptive therapy with Ganciclovir or Foscarnet will be administered, according to local standards, if CMV positive.
- Pre-emptive therapy with Rituximab will be administered to EBV-positive patients after gene therapy in case of repeated increase of EBV viral load, according to local standards.
- Erythrocyte and thrombocyte concentrates will be substituted according to local standard. The decision to administer erythrocytes or platelets transfusions should incorporate individual clinical characteristics of the patients and not simply be a reflexive reaction to the platelet count. All blood products will be leukocyte depleted and irradiated.
- The need for a platelet infusion will be evaluated by the Investigators based on several factors, including:
 - platelets <20 x 10⁹/L;
 - the presence of active bleeding;
 - stability of thrombocytopenia;
 - concurrent infection and febrile condition;
 - immune thrombocytopenic purpura;
 - use and response to thrombopoietin (TPO) receptor agonists;
 - presence of risk factors for bleeding (such as an upcoming invasive surgical procedure);
 - toxicity which may lead to an increased risk of bleeding;
 - subjects at risk of fall and trauma; and
 - overall clinical condition of the subject.
- Several factors are considered in deciding whether the interruption of IVIG can be stopped:
 - stable trough levels of IgG (immunoglobulin G) remaining at or above 5 g/L;
 - absence of symptoms of infections or positivity at laboratory tests for pathogens;
 - the presence of adequate levels of B cells in the peripheral blood;

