9.5. Improved platelet count and normalization of MPV

Increase in platelet count compared to baseline, considered as the mean of the (at least three) determinations performed in the 3 months before beginning of treatment. Patients will also be evaluated according to a stratification of the severity of thrombocytopenia in 5 groups (see Section 8.3.1, Table 5).

The individual longitudinal profile will be analyzed according to the planned follow up visit and including platelet counts collected for clinical reasons during follow up (in transfusion independent patients).

The determination of platelet count following procedures that may alter platelet number (thrombocyte infusion, TPO agonists etc.) will not be considered for evaluation.

Normalization of MPV compared to baseline will be evaluated at 1 year after gene therapy.

Assessment parameters: Platelet count and MPV.

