12.4. Efficacy endpoints

Primary efficacy endpoints

Overall survival

The Kaplan-Meier estimate of survival at 3 years from gene therapy will be obtained, with 95% Confidence Intervals, based on deaths by any causes related to disease. Survival will be also monitored as part of the long-term follow up.

Sustained engraftment of genetically corrected haematopoietic stem cells in peripheral blood and/or in bone marrow

The percentage of subjects who present at one year after gene therapy with adequate engraftment defined as $\geq 4\%$ CD34+ in the bone marrow or $\geq 10\%$ in peripheral blood T lymphocytes will be estimated and the 95% Confidence Intervals (CI) of this proportion will also be calculated. The description of the longitudinal profile over time of the percentage of gene corrected cells on both bone marrow and peripheral blood might be included as additional information.

Expression of vector-derived WASP

The percentage of subjects who present at one year after gene therapy with detectable vector-derived WASP expression will be estimated, with 95% CI.

Improved T-cell functions

The mean change between the pre-gene therapy and the 1-year values of in vitro T-cell proliferation upon stimulation with anti-CD3i will be calculated, with 95% CI, if appropriate. The description of the longitudinal profile over time of the levels of the in vitro T-cell proliferation might be included as additional information. The degree of correction (reached at 1, 2 and 3 years from gene therapy) with respect to normal control levels will also be described.

Antigen-specific responses to vaccinations

The percentage of subjects who respond to vaccination (see Section 9.4) performed > 1 year after gene therapy will be estimated, with 95% CI.

Improved platelet count

The percentage of subjects who improved the level of platelet count at 1, 2 and 3 years after gene therapy compared to baseline, shifting from one category to the subsequent as defined in Section 9.5, will be estimated, with 95% CI. The relative mean change in platelet count with respect to pre-gene therapy value will also be given. The description of the longitudinal profile over time of the platelet count might be included as additional information.

Secondary efficacy endpoints

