Response to vaccination will only be looked at in subjects who have completed the required schedule for the specific vaccination and have had a period of at least 90 days after their last IVIG infusion.

Reference values to define protective or positive responses are summarised below for each specific antigen.

Table 6 Reference values for protective response by antigen

Parameter	Protective response cut-off	Unit
Tetanus Toxoid	820	cpm
Tetanus IgG	0.4	IU/mL
Pneumococcus IgG	200	titre
Pneumococcus IgM	100	titre
Pertussis IgG Antibody	11	Arbitrary U
Hepatitis B Virus Surface Antibody	100	mU/mL
Hemophilus influenzae B Antibody	1	mg/L
Diphtheria IgG Antibody	0.4	IU/mL

A summary of response at any point within the first 3 years after GT as well as over the whole follow-up phase will be produced. In addition, the longitudinal profiles over time of responses to vaccinations will be described together with vaccinations in a listing.

A summary of the number of IVIG infusions per treatment phase will be presented along with the rate of infusions per year of observation.

A summary of time to sustained IVIG discontinuation will be produced for subjects who no longer need IVIG infusions. The cessation of sustained IVIG treatment is defined as a period of 3 months post gene therapy without IVIG treatment. The time to discontinuation will be presented in a table and Kaplan Meier plot including median time to discontinuation and 95% confidence interval.

Separate listings will be produced for patients requiring IVIG infusions and time to IVIG discontinuation (for those subjects who no longer need IVIG infusions).

9.1.6 Platelet counts and Mean Platelet Volume.

Absolute values of platelet count and mean platelet volume (MPV) as well as change from baseline will be calculated according to the planned follow up visits and including platelet count collected for clinical reasons during follow up (in infusion independent subjects). Baseline platelet count will be calculated as the median of the (at least three) determinations performed before beginning of treatment.

Normalization of MPV is defined as MPV within the normal range (MPV \geq 7.4 fL for children (< 18 years) and MPV \geq 9.1 fL for adults). Platelet count data obtained within 7 days following platelet infusions will not be considered for evaluation.

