Subjects will be also stratified according to the severity of thrombocytopenia before gene therapy in 5 groups (A, B, C, D and E) and the subject will be defined as improved if there is a positive shift (an increase in platelet count) from one group to the subsequent as shown in Table 7. If a subject has no values more than 7 days from a platelet infusion then they are imputed as being in group A.

Table 7 Stratification of platelet count according to severity of thrombocytopenia (count $\times 10^9/L$)

A	B	C	D	E
< 20	20 - < 50	50 - < 100	100 - < 150	≥ 150

The percentage of subjects who have improved platelet count over baseline at 1 to 8 years (annually) after gene therapy will be calculated with 95% CI.

The means for absolute values and change from baseline will be calculated with 95% CI each year after gene therapy for platelet count and MPV. There will also be accompanying summary statistics.

At 1-8 years after gene therapy the number of subjects with normal MPV will be summarised. The longitudinal profile over time of platelet count and MPV will be described by means of a listing and a plot. The listing will identify which platelet count data points were within 7 days after a platelet infusion as well as thrombocytopenia severity data.

Shift tables of platelet count (as in Table 7) and MPV compared to baseline will be presented for each year after gene therapy.

Median platelet counts will be summarised by baseline WASP expression (Reduced, Absent, Presence of Revertant (>5%)) by means of a bar graph at each year post gene therapy.

Arithmetic mean (and 95% confidence interval) values of platelet count and MPV data will be plotted over time.

A summary of the number of subjects with platelet infusions per treatment phase (See Table 3) will be presented along with the rate of infusions per year of observation.

A summary of time to discontinuation of sustained platelet infusions will be produced for subjects who no longer need platelet infusions. The cessation of sustained infusions is defined as a period of 3 months post gene therapy without a platelet infusion. The time to discontinuation will be presented in a table and Kaplan Meier plot including median time to discontinuation and 95% confidence interval.

Listings of both platelet infusions and time to platelet infusion discontinuation will also be created.

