10.2.5 Lentiviral Insertion Site Analysis (ISA)

The analysis and reporting of this exploratory safety endpoint will be detailed in a separate document that will be summarised within and appended to the CSR.

11 Data Not Summarised or Presented

The other variables and/or domains not summarised or presented are:

- Comments

These domains and/or variables will be available in the clinical study database and SDTM datasets.

12 Reporting Conventions

Display of decimals should follow the rules below:

- Minimum and maximum should be displayed to the same accuracy as the original data.
- Median and mean (arithmetic and geometric) and confidence intervals should be displayed to the accuracy of the original data + 1.
- Geometric CV will be reported to 1 decimal place.
- SD should be displayed to the accuracy of the original data + 2.
- For durations that are summarised, use 2 decimal places as the base. List to the same base number of decimal places.
- When summarising age, use 2 decimal places as the base. List to the same base number of decimal places.

Display of summary statistics should follow the rules below.

- There is no minimum n for mean, median, min and max. Present as follows:
 - For n = 1: Mean, median, min, max and geomean (where applicable).
 - For n ≥ 2: All summary stats for n=1, plus SD, LCL, UCL and geoCV (where applicable).

Calculating Geometric Summary Stats

To calculate geometric mean, first take the natural logarithm of the analysis value using the SAS log function, then calculate the mean of this [Mean], then exponentiate the mean: $e^{([Mean])}$ using the SAS exp function.

To calculate the geometric CV, first take the natural logarithm of the analysis value using the SAS log function, then calculate the standard deviation [STD], then calculate $100*\sqrt{e^{([STD]^2)}-1}$ using the SAS exp, ** (power), and sqrt functions/operators as appropriate.

13 Technical Details

Statistical evaluation will be performed by Veramed Limited.

The datasets will follow analysis dataset model (ADaM) data specifications.

All analyses will be performed using SAS version 9.4 or higher (SAS Institute, Cary, NC, USA).

14 Summary of Changes to the Protocol

There were two changes in the planned statistical analysis specified in protocol amendment 7 (Dated: 09JAN2015).

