16.3.3 Listings

Number	Title	Analysis Set
16.2.7.1	Listing of All Adverse Events	MS
16.2.7.2	Listing of Fatal Adverse Events	MS
16.2.7.3	Listing of All Serious Adverse Events	MS
16.2.7.4	Listing of Adverse Events Leading to Withdrawal from Study	MS
16.2.7.5	Listing of All Adverse Events Onset within 48 Hours from Infusion	MS
16.2.7.6	Listing of Predefined Adverse Event Groupings	MS
16.2.7.7	Listing of Relationship Between System Organ Class, Preferred Term, and Verbatim Text	MS
16.2.7.8	Listing of Adverse Events NCI CTCAE \geq 2 and Laboratory Features NCI CTCAE \geq 3 During the First 100 Days after Gene Therapy	MS
16.2.7.9	Listing of Hospitalisations	MS
16.2.8.1	Listing of Laboratory Data Outside Normal Range	MS
16.2.8.2	Listing of Laboratory Data	MS
16.2.8.3	Listing of Laboratory Tests and Associated Reference Ranges	MS
16.2.8.4	Listing of Vital Signs Data	MS
16.2.8.5	Listing of Absolute Neutrophil Count Response	MS

17 Appendix 2: Groupings for Medications, and Adverse Events related to Bleeds, Infections, Autoimmunity, Eczema or Suspected Malignancies

Grouping category	Terms
Medications	
Anti-infectives for systemic use	WHO-DD ATC 1 code J
Antineoplastic and immunomodulating agents	WHO-DD ATC 1 code L
Antimicrobials	WHO-DD coded term of: ACICLOVIR ACYCLOVIR AMOXICILLIN TRIHYDRATE;CLAVULANATE POTASSIUM AMOXICILLIN;CLAVULANATE POTASSIUM AMOXICILLIN;CLAVULANIC ACID AMPHOTERICIN B ANTIBIOTICS ANTIFUNGALS AZITHROMYCIN CEFAZOLIN CEFIXIME CEFTRIAXONE CEFTRIAXONE SODIUM CIPROFLOXACIN CIPROFLOXACIN HYDROCHLORIDE DAPSONE FLUCONAZOLE ITRACONAZOLE LEVOFLOXACIN MICAFUNGIN MICAFUNGIN SODIUM NYSTATIN PENTAMIDINE PENTAMIDINE ISETHIONATE SULFAMETHOXAZOLE;TRIMETHOPRIM VALGANCICLOVIR VALGANCICLOVIR HYDROCHLORIDE VORICONAZOLE
Blood and blood forming organs	WHO-DD ATC 1 code B
Dermatologicals	WHO-DD ATC 1 code D

Vaccines	WHO-DD ATC 2 J07
Infusion of platelets	WHO-DD coded term of PLATELETS, HUMAN BLOOD
Conditioning	WHO-DD coded terms of : RITUXIMAB BUSULFAN FLUDARABINE ANTITHYMOCYTE IMMUNOGLOBULIN
PBSC mobilization	Defined on PBSC eCRF page
IVIG infusion	WHO-DD ATC3 J06B is immunoglobulins.
Adverse Events	
Infections	MedDRA System Organ Class "INFECTIONS AND INFESTATIONS" Higher Level Group "MICROBIOLOGY AND SEROLOGY INVESTIGATIONS" in "INVESTIGATIONS" SOC Lower Level Terms 10003525 and 10022617 from SOC "RESPIRATORY, THORACIC AND MEDIASTINAL DISORDERS"

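### SAP 9.1.6 omits the protocol's exclusion of platelet counts following TPO agonists from a primary endpoint, and section 14 does not declare it

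*SAP*

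**What the plan says.** **Protocol.** Section 4.3.1(f) makes platelet count a primary efficacy endpoint, judged by movement between five severity groups. Section 12.4 takes the percentage of patients improved at 1, 2 and 3 years, "shifting from one category to the subsequent as defined in Section 9.5, will be estimated, with 95% CI". Section 9.5 sets the exclusion: "The determination of platelet count following procedures that may alter platelet number (thrombocyte infusion, TPO agonists etc.) will not be considered for evaluation". It gives no time limit. The same section defines baseline as the mean of at least three counts in the 3 months before treatment. Section 6.11 lists "use and response to thrombopoietin (TPO) receptor agonists" among the factors to weigh when deciding on a platelet infusion.

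**SAP.** Section 9.1.6 has one exclusion: "Platelet count data obtained within 7 days following platelet infusions will not be considered for evaluation". Its rule for patients without usable counts is tied to infusions: "If a subject has no values more than 7 days from a platelet infusion then they are imputed as being in group A". So is the listing flag: "The listing will identify which platelet count data points were within 7 days after a platelet infusion". Appendix 2 identifies infusions by "WHO-DD coded term of PLATELETS, HUMAN BLOOD" and has no grouping for TPO agonists. Sections 5.3.4 and 9.1.6 define the platelet baseline as a median of at least three pre-treatment counts, with no look-back window.

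Section 14 begins: "There were two changes in the planned statistical analysis specified in protocol amendment 7". Those two are the wider visit windows and the Day 1 convention. It then lists changes from later amendments. Its only platelet entry concerns the exploratory activation and morphology endpoint.

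**The concern.** This is an uncontrolled before-and-after comparison in 8 patients. If a drug that acts on platelet number is given near an assessment, the design cannot separate its effect from that of gene therapy. The protocol deals with this by discarding the affected counts.

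The SAP is not silent, which would leave the protocol rule standing. It states a specific and narrower rule, and a programmer who follows it will keep on-agonist counts. Because the protocol sets no time limit, the SAP is where the exclusion has to be made workable. It does that for infusions, with 7 days, and drops the rest. The affected outputs are the yearly percentage improved, the shift tables, and the mean platelet count and mean change from baseline.

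**Working it through.** **1. The rules side by side**

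| Item | Protocol 9.5 | SAP 9.1.6 |
|---|---|---|
| Counts after platelet infusion | Excluded, no time limit | Excluded for 7 days |
| Counts after TPO agonists | Excluded, no time limit | No rule |
| Other procedures that may alter the count | Excluded, open-ended | No rule |
| Baseline | Mean of at least 3 counts, last 3 months | Median of at least 3 counts, no window |

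SAP section 14 declares none of these differences. SAP section 3 bases the SAP on protocol version 12, which contains 9.5 as described. The SAP does limit counts taken for clinical reasons to infusion-independent subjects, but a patient on an agonist can be infusion-independent, so this does not remove on-agonist counts.

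**2. Scale.** The plan states no expected percentage, so there is no figure to reproduce. Inputs: n = 8 (protocol 5.1.3, SAP 6) and Wilson 95% intervals (protocol 12.5, SAP 9), with z = 1.96 and z² = 3.84. Assumptions: 7 of 8 patients improved in a given year under the SAP rule, and one of the 7 has only on-agonist counts that year.

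Limits = [p + z²/(2n) ± z·√(p(1−p)/n + z²/(4n²))] / (1 + z²/n)

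- SAP as written, 7/8: p = 0.875; (0.875 + 0.240 ± 1.96·√(0.01367 + 0.01501)) / 1.480 = 0.753 ± 0.224. Result 87.5% (52.9 to 97.8).
- Counts removed as in protocol 9.5, patient not evaluable, 6/7: p = 0.857; (0.857 + 0.274 ± 1.96·√(0.01749 + 0.01960)) / 1.549 = 0.731 ± 0.244. Result 85.7% (48.7 to 97.4).
- Patient scored as not improved, by analogy with the group A rule, 6/8: p = 0.750; (0.750 + 0.240 ± 1.96·√(0.02344 + 0.01501)) / 1.480 = 0.669 ± 0.260. Result 75.0% (40.9 to 92.9).

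The protocol's own rule therefore moves the estimate by 87.5 − 85.7 = 1.8 points. Scoring the patient as not improved moves it by 1/8 = 12.5 points. If the patient also has an off-agonist count in the window, the exclusion only changes which count is used, and the group may stay the same.

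**3. Direction.** Protocol 9.5 says only that such procedures may alter platelet number; I take an agonist's effect to be a rise. After gene therapy, that rise favours improvement. Before gene therapy, it raises the baseline and makes improvement harder to show.

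**4. Baseline (minor).** Two examples with assumed counts (×10⁹/L) and a follow-up count of 30, which is group B:

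- Counts 12, 15, 40: mean 67/3 = 22.3 (group B), median 15 (group A). The patient is improved under the SAP only.
- Counts 14, 16, 18 within 3 months and 30, 32, 34, 35 earlier: protocol mean 48/3 = 16 (group A), SAP median of all seven = 30 (group B). The patient is improved under the protocol only.

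The second example needs older counts in the database. The schedule lists only screening and baseline visits, and protocol 7.1 accepts pre-enrolment tests exceptionally. The direction is therefore indeterminate.

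**The case against.** - **Exposure is thinly supported.** TPO agonists are one of ten factors in an infusion decision. The protocol schedules none, and nothing places their use near a yearly assessment. This stands: the number affected may be zero.
- **A loss of 12.5 points per affected patient is not what the protocol implies.** A reader might infer it from n = 8. Protocol 9.5 removes the counts and does not score the patient as a failure. The 12.5-point figure requires extending the SAP's infusion-only group A rule, which neither document asks for.
- **The omission need not inflate the result.** A reader might infer that it does, but the protocol's exclusion is not limited to follow-up counts, and pre-treatment use would bias the other way.
- **The link from 12.4 is partial.** Section 12.4 cites 9.5 for the category shift, and 4.3.1(f) does not repeat the exclusion. This is fair, but 9.5 is the section that says how the endpoint is assessed, and its wording is explicit.
- **Silence in section 14 is not yet a breach.** Protocol 12.6 promises that changed methods will be documented in the study report, which is still to come. Table 14.1.4.1 and Listing 16.2.4.4 would show agonist use, and SAP section 7 calls all intervals nominal. These points make the problem checkable and limit its weight, but none corrects the reported percentage.
- **The rule comes late.** The study is open label, began in April 2010 and has two planned interim analyses, so a washout set now cannot be fully independent of the data. That supports showing results both ways.

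**Conclusion.** The conflict is established by the text: following the SAP exactly puts counts that protocol 9.5 bars into a primary efficacy percentage, without declaration. Its effect on the result is not established. It depends on how many patients took an agonist and when, which the documents do not give. Under the assumption of 7 of 8 improved and one affected patient, applying the protocol rule changes 87.5% to 85.7%. The fall to 75.0% belongs to a sensitivity analysis. The documents do not support a claim that the platelet result is inflated or that any patient was misclassified. The point should be fixed before the final analysis because the remedy is small and the endpoint is primary. The baseline change is a minor declaration item: a median is defensible, and its effect could go either way.

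**What to change.** - **SAP 9.1.6:** keep the 7-day infusion rule. Also exclude baseline and follow-up counts obtained on a TPO agonist, or within an analysis washout after it. The sponsor defines the washout and fixes it before the final database freeze. This is an analysis rule only.
- **Appendix 2 and platelet listing:** add a TPO-agonist term list and a flag for the affected counts.
- **No evaluable count:** treat that patient-year as not evaluable, with not improved as a sensitivity analysis. Do not impute group A at baseline, because any follow-up count of 20 or more would then count as improvement.
- **Comparability:** interim outputs may have used the present rule, so also show the percentage without the TPO-agonist exclusion.
- **Section 14:** declare the final exclusion rule and the change of baseline from mean with a 3-month window to median without one. Show the protocol-defined baseline as a sensitivity analysis.

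The cost is SAP wording, one term list, one flag and a few extra rows. Concomitant medications are already coded and listed (SAP 8.4 and 16.1.2), so no new data are needed. The reported percentage may change slightly.
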